11.1.2. Pharmacokinetic Analysis Set

The PK analysis set will consist of all subjects in the safety analysis set and who received at least one quantifiable whole blood concentration post-dose tacrolimus (Cohort 1) or for cyclosporin (Cohort 2) with no important protocol deviations or AEs thought to impact the analysis of the PK data. A subject may be excluded if vomiting occurs at or before 2x the median t_{max} for the dose group and treatment. Data from subjects for whom the pre-dose concentration is > 5% of C_{max} may be excluded for that treatment period.

The exclusion of any subjects or time points from the calculation of the PK parameters will be documented by the PK Scientist including the reason(s) for exclusion.

The available concentration data and PK parameter data for any subjects excluded from the PK analysis set will be listed only. Concentration data for subjects excluded from the PK analysis set will be presented in the individual figures of concentration versus time plots.

11.1.3. Randomised Set

The randomised set will consist of all subjects randomised into the study.

11.2. Methods of Statistical Analyses

11.2.1. General Principles

The statistical methodology below describes the statistical analysis as it is foreseen when the study is being planned.

If circumstances should arise during the study rendering the analysis inappropriate, or if in the meantime improved methods of analysis should come to light, different analyses may be performed. A separate SAP will not be written for the study. Any deviations from the statistical methodology defined in this protocol, reasons for such deviations and all alternative/additional statistical analyses that may be performed will be described in the CSR.

Such changes to analyses may be written into an abbreviated SAP, if appropriate. The verification and review of all statistical modelling assumptions will be documented appropriately.

All analyses discussed below will be replicated for both of the cohorts.

Data listings will be based upon the safety analysis set. All original and derived PK parameters will be summarised using the PK set. Demographic and disposition data will be summarised, using the safety set. Safety data will be summarised using the safety set.

All summaries done "by treatment" will be performed by actual treatment, rather than treatment to which a subject was randomised.

For each cohort, demographic and baseline data will be summarised for all subjects in the randomised, by sequence and overall. Pharmacokinetic data will be summarised by treatment, or treatment and time point, as appropriate. Adverse events will be presented by treatment and overall. Safety data collected at multiple occasions within the same period will be presented by treatment, time point and overall.

Frequency counts (number of subjects [n] and percentages) will be made for categorical variables. Descriptive statistics (n, mean, SD, median, minimum and maximum) will be calculated for continuous variables. Descriptive statistics will only be presented if $n \geq 3$. If no subjects have data at a given time point, then only $n = 0$ will be presented. If $n < 3$, only the n, minimum and maximum will be presented. The other descriptive statistics will be left blank.

The following rules will apply to any repeated safety assessments occurring within each treatment period:

- If the repeated measurement of a specific parameter occurs prior to IMP administration (Day 1), then the last obtained value prior to dosing will be used (as baseline) in the descriptive statistics and in the calculation of changes from baseline;
- If the repeated measurement of a specific parameter occurs after IMP administration (Day 1), then the first (non-missing) value after dosing will be used in descriptive statistics and in the calculation of changes from baseline.

The planned sequence for measurement of multiple assessments at the same time point is described in Section 3.1.1.

For safety assessments performed at screening and the follow-up, the following rules will apply for any repeated assessments:

- If the repeated assessment occurs at screening the last available value will be used in the summary statistics;

- If the repeated assessment occurs at the Follow-up Visit the first non-missing assessment will be used in the summary statistics.

All statistical analyses and production of tables, figures and listings will be performed using SAS® version 9.4 or later.

11.2.2. Missing Data

Missing dates and times in the AE data will be handled as described in Section 10.1.1. Concentrations that are non-quantifiable in the PK data will be handled as described in Section 10.2.2.

There will be no imputations of other missing data. All subjects will be included in the safety analyses as far as the data permit.

11.2.3. Subject Disposition

A randomisation listing will be presented and include the following: each subject's randomisation number, the subject's full enrolment number, the treatment to which the subject has been randomised and the country where the study centre is located.

Subjects and/or data excluded from the PK analysis set will be listed including the reason for exclusion. Subject disposition will be listed and summarised, and the summary will include the following information: number of subjects randomised and dosed, number and percentage of subjects dosed in the study, number and subjects completing study and number and percentage of subjects who were withdrawn (including reasons for withdrawal). Disposition data will be presented based on all subjects randomised.

Subject discontinuations will be listed including the date of study exit, sequence, period, treatment received, date/time discontinuation, and treatment/study discontinuation (including reason for discontinuation) information.

11.2.3.1. Demographic and Baseline Data

Demographic variables (age, gender, race, ethnicity, height, weight and BMI) will be listed by subject. Demographic characteristics (age, gender, race and ethnicity) and subject characteristics (height, weight and BMI) will be summarised separately for all randomised subjects. The denominator for percentages will be the number of randomised subjects.

Medical history data will be listed by subject including visit, description of the disease/procedure, MedDRA SOC, MedDRA PT, start date and stop date (or ongoing if applicable).

11.2.4. Prior and Concomitant Medication and Drug Administration

11.2.4.1. Prior and Concomitant Medication

Prior medications are those that started and stopped prior to the first dose of IMP; all medications taken after first dosing are considered as concomitant (including medications that started prior to dosing and continued after). Prior medication started within 3 months prior to the first dose of IMP will be recorded also in the concomitant medication module of ClinBase™. Prior medications that were started before 3 months of first dose of IMP will not be recorded.

Prior and concomitant medication will be listed by subject and will include the following information: reported name, PT, the route of administration, dose, frequency, start date/time, duration, stop date/time and indication. Prior and concomitant medication will be coded according to the Sponsor's drug dictionary.

The duration will be calculated as:

- Duration = end date/time – start date/time (+1 day, if time is not available)

The duration may be presented in hours or days in the listing depending on the applicability to the emerging data. For medications with partial or completely missing start date/times and/or end date/times, the duration will not be calculated.

Medications with missing or partial start date/time and/or end date/time such that it is not possible to classify as prior or concomitant will be considered as concomitant in the listings.

11.2.4.2. Drug Administration

Drug administration dates and times will be listed for each subject.

11.2.5. Safety and Tolerability

All safety data (scheduled and unscheduled) will be presented in the data listings. Continuous variables will be summarised using descriptive statistics (n, mean, SD, minimum, median, maximum). Categorical variables will be summarised in frequency tables (frequency and proportion). The analysis of the safety variables will be based on the safety analysis set.

Safety measurement with start date/time at the time of or after dosing (for each specific treatment) until the next treatment/dose or until Follow-Up Visit will be assigned to the specific treatment/dose (including washout period).

Adverse events will be summarised by SOC and PT using MedDRA vocabulary. Furthermore, listings of SAEs and AEs that led to withdrawal will be made and the number of subjects who had any AE, SAEs, AEs that led to withdrawal, and AEs that led to death will be summarised. Serious adverse events that occur before dosing will be reported separately.

Tabulations and listings of data for vital signs, clinical laboratory tests and ECGs will be presented. Any new or aggravated clinically relevant abnormal medical physical examination finding compared to the baseline assessment will be reported as an AE. Data will be summarised for the observed values at each scheduled assessment, together with the corresponding changes (and/or percentage change) from the baseline when baseline value exists, by treatment. Clinical laboratory data will be reported in Système International units in the CSR.

Out-of-range values for safety laboratory will be flagged in individual listings as well as summarised descriptively using agreed standard reference ranges and/or extended reference ranges (eg, AZ, program, or laboratory ranges).

11.2.6. Pharmacokinetics

All PK concentration, parameter summaries and statistical analyses will be presented for the PK analysis set, unless otherwise specified. The PK concentration and parameter listings will be presented for the safety analysis set and will include all reportable individual PK results. Any PK concentration and parameter data not included in the PK statistical analyses will be included in the listings and flagged with an appropriate footnote.

A listing of PK blood sample collection times, as well as derived sampling time deviations and concentrations at each protocol scheduled time point will be provided. Whole blood concentrations will be summarised by treatment and nominal time points descriptively. The PK parameters will be summarised by treatment using appropriate descriptive statistics.

The listings, summaries and figures will be presented in accordance with the most recent version of the AstraZeneca Corporate CSRHLD Standards and the Final version of the TFL shells for this study. This include the applicable descriptive statistics, handling of individual concentrations below the LLOQ for listings, descriptive statistics and figures, and precision and rounding rules for concentrations and PK parameter data.

Individual concentrations with time deviations of $\geq \pm 10\%$ from the protocol scheduled time, will be used in the PK analysis but will be flagged for exclusion from the summary tables and corresponding figures.

Protocol scheduled times will be used to present the PK concentration summary tables and corresponding gmean concentration-time figures.

11.2.6.1. Graphical Presentation of Pharmacokinetic Data

Individual, combined individual, and gmean plots will be presented. All gmean plots or combined individual plots showing all subjects by treatment will be based on the PK analysis set. Separate plots for each Cohort will be provided. Individual plots by subject will be based on the safety analysis set.

For consistency, the plasma concentration values used in the gmean data graphs will be those given in the descriptive statistics summary table for each time point.

Individual plasma concentrations versus actual elapsed time after dose will be plotted on both the linear and semi-logarithmic scale with both treatments overlaid on the same plot and separate plots for each subject, and separate plots for each cohort.

Combined individual plasma concentration versus actual times will be plotted on both the linear and semi-logarithmic scale. Plots will be grouped by treatment and separate plots for each cohort.

The gmean plasma concentration (-/+gSD) versus nominal sampling time will be plotted on both the linear and semi-logarithmic scale with treatments overlaid on the same figure, and separate plots for each cohort.

11.2.6.2. Statistical Analysis of Pharmacokinetic Data

The below analyses will be performed for each of the 2 cohorts.

The difference in mean PK parameters (C_{max} , AUC_{inf}) for the 2 cohorts will be analysed using a mixed effects model following a natural logarithmic transformation of the individual PK parameters, with period, treatment and sequence as fixed effects, and subject nested within sequence as random effects. Least-squares means (LSM) for each treatment, the difference thereof, and the corresponding 2-sided 90% confidence intervals (CIs) for the log-transformed values will be presented. The corresponding geometric LSM for each treatment, the ratio thereof, and the 2-sided 90% CI will be estimated and presented as well.

The limits for the 90% CIs for the geometric mean ratio will be compared to the pre-specified interval (0.8000% to 1.2500%) for conclusion of no DDI (ie, if the CI lies entirely within the predetermined 0.8 and to 1.25 range, it will be concluded that SZC has no meaningful effect on the PK for tacrolimus/cyclosporin).

Statistical analysis will be done by using PK analysis set.

This mixed effects statistical model will be repeated for the secondary PK variables of AUC_{last} , $t_{1/2\lambda_z}$, and t_{max} , for both cohorts.

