Sodium zirconium cyclosilicate (SZC), is an oral, non-polymer inorganic cation-exchanger that has been approved as a novel therapy for the treatment of hyperkalaemia. It selectively captures potassium ions in exchange for sodium and hydrogen ions in the gastrointestinal lumen, thereby reducing serum potassium concentration and removing potassium from the body through increased faecal excretion. Sodium zirconium cyclosilicate exerts its effect locally and is not absorbed systemically. Due to its insoluble, inorganic, and crystalline properties, SZC is not absorbed or metabolised by the body and therefore no metabolic or transporter-based drug-drug interactions (DDIs) are anticipated in association with SZC treatment. However, SZC can bind to hydrogen ions which may result in increased pH in acidic environments such as the stomach. In general, an increase in gastric pH can alter the solubility of drugs with pH-dependent solubility and may result in an altered absorption profile of the drugs. Results from a Phase 1 study performed in healthy subjects to examine the potential for DDIs between SZC and a set of 9 compounds showed that co-administration of SZC affected the pharmacokinetics (PK), primarily the C_{max} values, of 5 compounds tested (Study ZS-009).

This study will investigate if the PK of tacrolimus and cyclosporin may be altered by the increased gastric pH resulting from SZC co-administration.

Number of Subjects Planned

A total of 60 subjects will be randomised (30 per cohort) to ensure at least 56 evaluable subjects (28 subjects per cohort) at the end of the last treatment period.

Study Period

Estimated date of first subject enrolled: December 2020 (signing of informed consent).

Estimated date of last subject completed: March 2021.

Study Objectives

Primary Objective:

- To assess the effect of co-administered SZC on the PK of tacrolimus and cyclosporin in healthy subjects as described by C_{max} and AUC_{inf}.

Secondary Objectives:

- To assess the effect of co-administered SZC on the PK of tacrolimus and cyclosporin in healthy subjects, as described by AUC_{last}, t_{1/2λ_z}, and t_{max}.
- To examine the safety and tolerability of co-administration of SZC and tacrolimus/cyclosporin as compared to tacrolimus/cyclosporin alone in healthy volunteers.

Study Design

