Trade Name:	Lokelma™	Prograf	Sandimmun Neoral/Optoral
Manufacturer:	AstraZeneca	Astellas Pharma	Novartis
Formulation:	Powder for oral suspension	Hard capsules	Soft capsules
Strength/concentration:	[CCI] sachet	[CCI]	[CCI]
Dose:	[CCI]	[CCI]	[CCI]
Route of administration:	Oral	Oral	Oral
Specific device for drug administration, if applicable:	Not applicable	Not applicable	Not applicable
Regimen:	Single dose of [CCI] consisting of 3 sachets suspended in 45 mL of water	Single dose of [CCI]	Single dose of [CCI]
Special handling requirements:	Not applicable	Not applicable	Not applicable

Outcome Endpoints

Pharmacokinetic Endpoints:

Where possible, PK parameters will be assessed for tacrolimus and cyclosporin on whole blood samples.

- Primary PK parameters: C_{max}, AUC_{inf}
 - AUC_{inf} and C_{max} measured for each subject and each visit on which PK data are collected.
- Secondary PK parameters: AUC_{last}, t_{1/2λ_z}, t_{max}

- AUC_{last}, t_{1/2λ_z}, and t_{max} measured for each subject and each visit on which PK data are collected.

Additional PK parameters may be determined where appropriate.

Safety and Tolerability Endpoints:

Safety and tolerability variables will include

- Adverse events, vital signs (systolic and diastolic BP, pulse, and tympanic temperature), 12-lead ECGs, laboratory assessments (haematology, clinical chemistry, and urinalysis).

Statistical Methods

Presentation and Analysis of Pharmacokinetic Data:

All PK concentration, parameter summaries and statistical analyses will be presented for the PK analysis set, unless otherwise specified. The PK concentration and parameter listings will be presented for the safety analysis set and will include all reportable individual PK results. Individual PK concentration and parameter data for any subjects not included in the PK statistical analyses will be included in the listings and flagged with an appropriate footnote.

A listing of PK blood sample collection times, as well as derived sampling time deviations and concentrations at each protocol scheduled time point will be provided. Whole blood concentrations will be summarised by treatment and nominal time points descriptively. The PK parameters will be summarised by treatment using appropriate descriptive statistics.

Individual concentrations with time deviations of $\geq \pm 10\%$ from the protocol scheduled time, will be used in the PK analysis but will be flagged for exclusion from the summary tables and corresponding figures.

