11.4. Determination of Sample Size

CCI

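### The no-interaction limits in Section 11.2.6.2 carry stray percent signs and contradict, by a factor of 100, the limits given later in the same sentence

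*Protocol*

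**What the plan says.** Section 11.2.6.2 of the protocol analyses Cmax and AUCinf in each cohort with a "mixed effects model following a natural logarithmic transformation of the individual PK parameters". Results are back-transformed: "The corresponding geometric LSM for each treatment, the ratio thereof, and the 2-sided 90% CI will be estimated and presented as well". The quantity used for the decision is therefore a ratio, whose value under no interaction is 1.

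The decision rule is one sentence. It begins with "The limits for the 90% CIs for the geometric mean ratio", says that these will be "compared to the pre-specified interval (0.8000% to 1.2500%) for conclusion of no DDI", and then explains the rule in parentheses: no meaningful effect of SZC is concluded "if the CI lies entirely within the predetermined 0.8 and to 1.25 range".

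Two other places bear on the point. Section 11.2.1 states that there will be no separate SAP. An abbreviated one is optional and is meant for changes to the analyses. The statistical part of the synopsis gives no acceptance interval, and the text under "11.4. Determination of Sample Size" is redacted.

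**The concern.** One threshold is stated twice in one sentence, and the two statements do not agree. With percent signs the limits are hundredths of what they are without them. The version with the percent signs is the one labelled as pre-specified. The usable version appears only in the parenthetical explanation, and its wording is itself garbled (it has both an *and* and a *to* between the limits).

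The sentence governs Cmax and AUCinf in both cohorts, that is 2 × 2 = 4 comparisons, and it is the only statement of the criterion that can be seen. Section 1.2 describes both drugs as having a narrow therapeutic range, so the limits behind a claim of no meaningful effect should not be open to question. Since no separate SAP is planned, a correction cannot be assumed to follow elsewhere.

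**Working it through.** **Inputs.** Bracketed limits 0.8000% and 1.2500%, and restated limits 0.8 and 1.25 (both Section 11.2.6.2). Evaluable subjects: 28 per cohort (synopsis). The within-subject CV, assumed true ratio and power are not visible because the sample-size text is redacted, so no sample size or power can be reproduced. For illustration only, a within-subject CV of 15% to 50% is assumed.

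**Step 1: put both statements on the ratio scale.**
- 0.8000% = 0.8000/100 = 0.008, and 1.2500% = 1.2500/100 = 0.0125.
- 0.8/0.008 = 100 and 1.25/0.0125 = 100. Both limits are off by the same factor.

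**Step 2: see which statement suits a ratio of geometric means.**
- ln(0.8) = −0.2231, ln(1.25) = +0.2231 and 1/0.8 = 1.25. The restated range is symmetric about a ratio of 1 on the log scale.
- ln(0.008) = −4.8283 and ln(0.0125) = −4.3820. The log width is 0.446, the same as for the restated range, but the geometric centre is √(0.008 × 0.0125) = 0.01.
- The literal interval therefore describes a fall in exposure of between 100 × (1 − 0.0125) = 98.75% and 100 × (1 − 0.008) = 99.2%. That cannot be meant as no interaction.

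**Step 3: apply both intervals to plausible results.** For a balanced two-period cross-over, the 90% CI is exp{ln(GMR) ± t(0.95, n − 2) × s_w × √(2/n)}, with s_w = √ln(1 + CV²) and n = 28.

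| Assumed CV | 90% CI at ratio 1 | Within 0.8 to 1.25 | Within 0.008 to 0.0125 | 90% CI at ratio 0.01 | Within 0.008 to 0.0125 |
|---|---|---|---|---|---|
| 15% | 0.934 to 1.070 | yes | no | 0.00934 to 0.0107 | yes |
| 30% | 0.875 to 1.143 | yes | no | 0.00875 to 0.01143 | yes |
| 50% | 0.806 to 1.240 | yes | no | 0.00806 to 0.0124 | yes |

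A result centred on no effect passes the restated range at each of these CVs and fails the bracketed one at each. The last two columns show that the literal interval is not empty: a ratio near 0.01 would satisfy it.

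**The case against.** The strongest reply is that the sentence corrects itself. The parenthesis opens with *ie*, so it explains the bracket and contains the actual instruction. It is on the scale of the quantity being compared, its limits are reciprocals, and its digits match the bracket, which already uses a four-decimal ratio format. A stray percent sign is the only sensible reading, and it is hard to see an analyst programming limits that declare no interaction when exposure falls by about 99%. All of this stands, and it is why the point is minor.

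Several stronger readings are tempting, and the protocol does not support them:

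- A reader might infer that no confidence interval could ever meet the printed limits. Step 3 shows otherwise: an interval around 0.01 would. The accurate statement is that none near a ratio of 1 would.
- A reader might infer that a ratio of exactly 1 fails the rule. It fails the bracketed interval, but the rule as a whole includes the explanatory clause, under which 1 passes.
- A reader might infer that the clinical study report or the table shells carry the error. Neither is shown.
- A reader might infer that nothing later could correct it. Section 11.2.1 leaves room for an abbreviated SAP, and Section 11.2.6 refers to final table shells. What can be said is that no separate SAP is planned.
- A reader might infer that the interval is stated nowhere else at all. That cannot be checked, because the sample-size text is redacted. It is stated nowhere else in the visible text.

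What the reply does not remove is the contradiction itself. The digits and percent signs are intact, so neither redaction nor text extraction plausibly explains it.

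**Conclusion.** The point holds as a self-contradiction in the primary decision rule. The bracketed limits are 100 times too small on the ratio scale and conflict with the 0.8 to 1.25 in the same sentence. The intended limits are recoverable from that sentence, so this is a minor correction, although a certain one. The model, the 90% confidence level and the sample size are untouched, and no computed result would change.

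The factor of 100 rests on unit conversion alone and needs no assumption. Only the illustrative intervals depend on assumed values: a within-subject CV of 15% to 50%, 28 evaluable subjects per cohort and balanced sequences. The conclusion does not depend on them.

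**What to change.** In Section 11.2.6.2, give the interval in one form, **0.8000 to 1.2500 (80.00% to 125.00%)**, and reword the parenthesis so that it repeats the same limits: the CI lies entirely within 0.8000 to 1.2500. This uses the protocol's own restated limits and introduces no new threshold. When the table shells and report text are prepared, check that they take the corrected form.

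The cost is one line of protocol text, suitable for an administrative amendment. It needs no additional data, subjects or analysis.
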